**Aim 3:** To examine if changes in the following potential mechanisms of change variables mediate treatment effects (e.g., Step One and standard TF-CBT) on child PTSS and impairment: (a) fear habituation: decreases in child’s fear-based arousal; (b) cognitive changes: reductions in child’s negative trauma-related cognitions; (c) inhibitory learning: child’s decrease in expectancy of negative outcomes; and (d) fear toleration: extent of child’s toleration of fear activation.

**3.1. Hypothesis:** Decreases in children’s fear-based arousal, improvements in negative trauma-related cognitions, decreases in children’s expectancy of negative outcomes, and changes in fear toleration over time will mediate Step One and standard TF-CBT treatment outcomes in PTSS and impairment.

**3.2. Secondary Hypothesis:** The mechanisms of change (e.g., a, b, c and d in Aim 3) will occur during all components of treatment but greater changes in these processes will occur during more direct exposure activities (e.g., imaginal and *in vivo* exposure in Step One) than less direct exposure activities (e.g., developing a trauma narrative in Standard TF-CBT) and during coping skills in both treatments.

**Aim 4:** To examine the economic cost of delivering SC-TF-CBT versus standard TF-CBT.

**4.1. Hypothesis:** Stepped Care TF-CBT will be more cost-effective than standard TF-CBT.

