**a.4. Understanding Mechanisms of Change Within Stepped Care Can Lead to More Targeted, Optimized Interventions.** While recent adult trials on trauma-focused treatment examined changes during treatment that account for improved outcomes,[36-38] research on mechanisms of change in child trauma-focused treatment is limited. Despite the trials on TF-CBT, our understanding of mechanisms of change is limited.[39] For children needing to be matched directly to TF-CBT or to Step One within SC-TF-CBT, targeting the mechanisms of change could optimize treatment such that clinicians could target these processes and monitor progress, thus tailoring treatment delivery. The one dismantling study on TF-CBT components suggest that although all children improved across outcomes, there were differential responses based on receiving the trauma narrative only (e.g., less parental distress about the abuse) versus coping skills only (e.g., improvements in parenting practices).[26] This study did not examine within session mechanisms of change and the authors suggest that by virtue of discussing coping skills in the context of trauma, exposure occurs. In the proposed study, we will examine in Step One and TF-CBT four potential mechanisms of change (e.g., fear arousal, maladaptive cognitions, expectancy of negative outcomes, fear toleration) based on two prevailing theories (e.g., emotional processing theory and inhibitory learning; Primary Aim 3). Step One, a parent-led therapist-assisted treatment and TF-CBT include coping skills (e.g., affect management, stress management) and exposure, but exposure methods are more direct in Step One (e.g., imaginal and *in vivo*) than TF-CBT (e.g., gradual trauma narration). Patterns of change among the potential mechanisms of change during different treatment components will be explored. Understanding mechanisms of action will have implications not only for these two trauma interventions, but will be applicable more broadly to therapies for anxiety.

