change in HR and SC responses to the interview relative to baseline. 2) A subjective unit of distress (SUD) scale which is commonly used will be rated by the child using a developmentally appropriate SUD rating (i.e., “scary feeling score,” 0-3 or 4). Prior research with young children as well as our experience suggests that children age 4 and older understand the rating scale and can provide these data. Similar to our pilot work, children will provide six ratings during exposure or trauma-related activities and parents will record these ratings. In TF-CBT, the child ratings will be recorded by the therapist. The first rating will occur before the exposure/activity, four during the activity with the highest being recorded as the peak rating and one after the exposure/activity. Changes in trauma-related negative appraisals: The *Post-Traumatic Cognitions Inventory-child version (CPTCI)*, is a 25-item child report of negative trauma-related cognitions. The CPTCI has demonstrated excellent psychometrics and no age-related differences in scores for children ages 6-18. The measure will be administered with children ages 6 to 12 (~78% of the sample). Expectancy of negative outcomes (ENOs): The ENOs measure, modified from [name] et al. and similar to Deacon et al., is a 3-item parent report of the child’s perceived expectancy of a negative outcome that is rated (0 to 100) before and after the trauma-related activity. Children’s fear toleration (CFT): Similar to Deacon et al., parents will rate (0-100) the extent of the child’s fear toleration when participating in the trauma-focused activity. Therapeutic worry and alliance will also be examined as potential mechanisms of change which will be measured using the treatment worry questionnaire at baseline only (child and parent version) and the Therapeutic Alliance Scale for Children (TASC, parent, child, and therapist version) administered the same assessment time periods as the HR and SC (i.e., Weeks, 0, 2,4 = Step One & 0,5,8= TF-CBT and at post-assessment) (Keeley et al. 2011). As indicated in Table 1, the mechanism of change measures will occur at post-assessment too. The “trauma-related activity” will be a 5 minute semi-structured interview that consists of the same guide that is used during the HR and SK test. After these measures are completed the parent and child will be asked independently 6 questions about their experiences talking about what happened, including how they may have changed. These responses will be used to triangulate the quantitative measures.

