**Within session ratings.** Parents will rate fear toleration and negative expectancy after each trauma-related activity in therapy sessions and parent-child meetings. As in previous NIH-funded clinical trials (PI: [name], study therapist [name], R34MH070827-01A1; 1RC1MH-088969-01), therapist-directed sessions will be video taped. We will systematically identify the child’s participation in the trauma-focused activity within each session and have parents review that segment via video (~15 min.) during the beginning of the time when the parent meets with the therapist. These research procedures will not significantly influence treatment outcome as discussing with the parent what the child completed in therapist-led sessions is current protocol for both treatments, and similar procedures have been used in previous trauma-focused clinical trials with children 3-12. This procedure allows the parent to have direct observation of the child and allows the parent time to process the observations with the therapist. Viewing video segments will not be needed when there are conjoint sessions. For the at-home parent-child meetings, the parent will complete the ratings immediately after the meetings. Children will complete the *CPTCI* at the beginning of Weeks, 0, 2,4 in Step One & 0,5,8 in TF-CBT and the SUDS rating during treatment. For Step One, measures will be in the parent’s *Stepping Together* book, and therapists will collect these measures at each meeting and will remind parents about the measures during the phone meetings. Since Step One and TF-CBT occur within different timeframes (6wks vs. 3mo), the physiological measures will be administered based on when components are covered and during scheduled in-office visits for Step One patients: at session 1, after the coping skills components, and after four exposures in Step One or the trauma narrative in TF-CBT (Table 1). The frequency of four potential mechanism of change measures (e.g., fear based arousal measure (subjective unit of distress), trauma-related negative appraisals, expectancy of negative outcomes, and fear toleration) will be 12 for both conditions. Step One patients will not complete these measures during parent-child meetings 1 and 2 as these meeting occur directly after the first therapist meeting.

**c.6.7. Fidelity Measures.** All of the fidelity measures were successfully utilized in the pilot trials of SC-TF-CBT.

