**Primary Aim 3:** We will examine four potential mechanisms of change on both Step One and TF-CBT including fear arousal, maladaptive cognitions, expectancy of negative outcomes, and fear toleration. The analysis of mechanism of change will have two phases. First, we will run univariate latent difference score (Goldstein, #1) models on the longitudinal observations of potential mediator and outcome variables. Since the fear-arousal variables (HR and SC) that both assess sympathetic nervous system activation are typically correlated, and combining physiological responses into single indices is common (e.g.,), we will attempt to combine them into a single index. LDS incorporates features of latent growth curve modeling and cross-lagged regression models and is appropriate in research on mechanisms of change. We will compare univariate LDS models for time invariant and time-varying proportional coefficients as well as a no change score LDS model to find the model that best depicts the mechanism. The model selection process will run independently across all potential mediators and outcome variables. Second, we will run bivariate LDS by pairing between two univariate LDS models that have been identified. These pairings include mediator-mediator, mediator-outcome, and outcome-outcome types. We will identify coupling pattern by comparing three candidate models (within the bivariate LDS models): no coupling between the two series, unidirectional coupling in which the change in one variable leads to the other, and bidirectional coupling or cross lagged pattern. For the secondary hypothesis 3.2., we will add a time varying qualitative indicator for direct exposure activities and its interaction with the change component. A significant interaction term indicates the mechanisms are different for the more direct (i.e., Step One) and less direct exposure activities (i.e., TF-CBT). We will also use open coding methods to capture a range of categories related to children and parents experience of talking about the trauma narrative (a trauma related activity used during the mechanism of change measures) and changes that may have occurred during treatment. Thematic content analysis (Patton, 2002; Corbin & Strauss, 2008) will be used to establish the range of participants' experiences and changes.

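### The Hypothesis 3.2 interaction is read as direct versus less direct exposure, but that between-treatment contrast is confounded with the delivery package, and the amendment does not say how 3.2 is tested

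*Combined protocol and SAP*

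**What the plan says.** - **Hypothesis 3.2 (section 2, Aim 3)** expects larger mechanism changes during direct exposure (imaginal and in vivo, with Step One as the example) "than less direct exposure activities (e.g., developing a trauma narrative in Standard TF-CBT) and during coping skills in both treatments". There are therefore two comparators: less direct exposure, and coping work in both treatments.
- **Section a.4** says that "Step One, a parent-led therapist-assisted treatment and TF-CBT include coping skills (e.g., affect management, stress management) and exposure", but that "exposure methods are more direct in Step One".
- **Section c.8.3, Primary Aim 3** says "we will add a time varying qualitative indicator for direct exposure activities and its interaction with the change component". It then fixes the reading: "A significant interaction term indicates the mechanisms are different for the more direct (i.e., Step One) and less direct exposure activities (i.e., TF-CBT". It names no arm, arm-by-change or phase term.
- **Section c.9** gives power of .57 for 3.2, for a difference in predictive strength between the two conditions (0.15 versus 0.45, or .00 versus .30).
- **Section c.5.1** says that Step One, Step Two and standard TF-CBT all address coping skills, trauma narrative and cognitive processing.
- **Section c.6.5** has parents record the child's distress ratings, but "In TF-CBT, the child ratings will be recorded by the therapist".
- **Section c.6.6** has parents rate fear toleration and expectancy straight after at-home meetings. For therapist-directed sessions, other than conjoint ones, the plan will "have parents review that segment via video".
- **The amendment of 2.11.2022** replaces latent difference score models with linear mixed models for Aim 3. The group contrast is standard TF-CBT (0) against Step One responders (1). Hypothesis 3.2 and the activity indicator are not mentioned.

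**The concern.** The reading rule turns a difference between two treatments into a statement about one ingredient of them. Step One and TF-CBT differ in how direct the exposure is. They also differ in leader (parent or therapist), setting (largely home or office), pace (6 weeks or 3 months, section c.6.6) and, for the distress, toleration and expectancy ratings, in who records them or how they are made. Randomisation protects the comparison of whole packages. It does not say which component caused a difference, and a larger sample would not help.

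A significant term could therefore arise from parent-led delivery or rating mode and still be reported as a finding about directness of exposure. Section a.4 expects the mechanism results to inform how clinicians tailor treatment and to apply to anxiety therapies more broadly. The rule also leaves the coping-skills comparator, which is half of 3.2, without a stated test.

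**Working it through.** **1. Which contrast is powered?** Inputs from c.9: 92 per group and coefficients 0.15 versus 0.45 or .00 versus .30. Alpha is not stated for 3.2, so 0.05 two-sided is an assumption.

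Standardised slopes: power = Φ{(b2 − b1)/√[((1 − b1²) + (1 − b2²))/92] − 1.96}.
- 0.15 versus 0.45: 0.30/√(1.775/92) = 2.160, and Φ(0.200) = 0.579.
- 0.00 versus 0.30: 0.30/√(1.91/92) = 2.082, and Φ(0.122) = 0.549.

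Fisher z with standard error √(2/89) gives 0.605 and 0.542, mean 0.573. One-sided versions give 0.65 to 0.72 and do not fit. The plan's .57 is thus approximately reproduced as a comparison of 92 with 92 children, that is, of the two arms. The plan gives no formula, so this supports the reading but does not prove it.

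**2. Is the indicator the same variable as arm?** Suppose it is 1 only at k of 12 occasions in Step One (12 is the measurement frequency in c.6.6; k is an assumption). With equal arms, the proportion of rows equal to 1 is q = k/24, and its correlation with arm is √[q/(1 − q)].

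| k | q | correlation with arm |
|---|---|---|
| 4 | 1/6 | 0.45 |
| 6 | 1/4 | 0.58 |
| 8 | 1/3 | 0.71 |
| 12 | 1/2 | 1.00 |

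Intercept, arm and indicator have full rank (3) for k = 4, 6 and 8. Rank falls to 2 only if every Step One occasion is coded direct. Under this coding, however, no TF-CBT row is ever 1.

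**3. What does the term estimate without arm terms?** It compares coupling at Step One direct occasions with coupling pooled over all other rows. Take k = 6, no effect of directness, and coupling constant within arm.
- Arms at 0.45 and 0.15: pooled value (6 × 0.45 + 12 × 0.15)/18 = 0.25, so the term is 0.45 − 0.25 = 0.20.
- Arms at 0.30 and 0.20: pooled value (6 × 0.30 + 12 × 0.20)/18 = 0.233, so the term is 0.067.

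Both terms are non-zero purely because the arms differ.

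**4. How often would it be significant?** Simulation: 1,000 replicates, 92 per arm, 12 occasions, k = 6, a regression coupling model in place of the latent difference score model, a cluster-robust test, and no directness effect.

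| Coupling by arm | No arm terms | Arm and arm × change added |
|---|---|---|
| 0.45 vs 0.15 | 94.3% | 5.5% |
| 0.30 vs 0.20 | 25.4% | 5.7% |
| 0.30 vs 0.30 | 6.4% | 5.8% |

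The rates depend on the number of occasions and the variances assumed. They show the direction and potential size of the problem and do not forecast this trial's error rate.

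**5. What does the term mean once arm terms are in?** It compares Step One exposure with the other Step One sessions. That answers the coping comparator in Step One. It does not compare direct exposure with TF-CBT narration.

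**6. The amendment.** Its contrast is explicitly by group, and one group is defined by response after randomisation. If the pilot rate in c.1.3 held (38 of 49 responded), 11/49 = 22.4% of children assessed after Step One would be left out of that group, with no matching exclusion in standard TF-CBT.

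**The case against.** A reader might infer that the indicator is simply treatment arm under another name, so that directness and arm are completely aliased at any sample size. The documents do not support that. The indicator is described as time-varying and, as step 2 shows, is separable from arm unless every Step One occasion is coded direct. Section c.5.1 says Step One also addresses trauma narrative, the plan's own example of less direct exposure, so a comparison of exposure with narrative within Step One may be possible. Section a.4 describes the difference between treatments as one of degree. Children who step up also receive TF-CBT (c.3.1), although that comparison is tied to non-response, non-adherence or new trauma and to order, and the documents do not clearly say that mechanism measures are taken in Step Two.

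Three further points have weight. Rating mode cannot explain every mechanism: negative cognitions are reported by the child, and heart rate and skin conductance are recorded by a device, in both treatments. Hypothesis 3.2 is secondary, its patterns are described as exploratory, and its power is openly called moderate. The amendment replaces the model to which the reading rule belonged, so the quoted test may no longer be operative.

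What these points leave standing is narrower. The stated reading still equates exposure type with treatment and names no arm term. Leader, setting and pace differ for all the mechanisms. The amendment neither withdraws 3.2 nor supplies an unconfounded test of it.

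**Conclusion.** The concern holds in a limited form. A Step One versus TF-CBT interaction supports a statement about two delivery packages. It does not support one about directness of exposure. Without arm terms, a difference in coupling between arms alone could make the term significant anywhere from about a quarter of the time (0.30 versus 0.20) to nearly always (0.45 versus 0.15), given the simulation's assumptions: 6 direct occasions of 12, independent occasions and a regression stand-in. Exposure versus coping within Step One remains testable, and exposure versus narrative within Step One may be.

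Whether the rule was ever applied cannot be told from the amendment. If the amended group contrast was used to address 3.2, it carries the same confounding and adds selection of responders after randomisation. This is a minor point for a secondary hypothesis, but one where following the plan as written could give a wrong conclusion.

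**What to change.** 1. Code each session or parent-child meeting as coping, narrative or direct exposure, by the same rule in each arm, and say how Step Two sessions are handled.
2. Include arm, session order or phase, and their interactions with change. Coping work comes before exposure or narrative in the measurement schedule of c.6.6, so order needs its own term. A phase variable defined as coping versus exposure would merely duplicate session type, in which case use a trend over sessions.
3. Test 3.2 by within-arm contrasts: exposure versus coping and, if the content allows, exposure versus narrative in Step One; narrative versus coping in TF-CBT.
4. Report any Step One versus TF-CBT term only as a difference between delivery packages.
5. State whether 3.2 was tested under the amended mixed models and, if so, with which term and in which children. Describe any comparison using Step One responders as non-randomised.

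The cost is somewhat more modelling on data already planned. Before relying on the within-arm contrasts, confirm that ratings exist for coping sessions: Table 1 lists them for every session or meeting, while c.6.5 ties the distress ratings to exposure or trauma-related activities. The physiological measures, with three in-treatment time points, allow only a coarse version. What is given up is attributing a between-arm result to directness of exposure.

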## Amendment to the analysis plan 2.11.2022

**Aim 1.** We applied linear mixed-effect models (LME; SAS Institute Inc, 2015) with repeated measures to detect whether the two treatments performed differently at post-, 6- and 12-month assessments. Instead of 5% alpha we used a more stringent 2.5% alpha (Piaggio et al, 2012) for the non-inferiority analysis with the .41 margin. For the non-inferiority margin for the PCL-5, the clinically significant change threshold is 10 points although adult PTSD trials have used -5 (Foa et al., 2019) to -10 (Mathersul et al., 2019) points. We used -8.8 as the margin which was based on an expert panel and prior studies with adults (Acierno et al., 2017). Due to attrition (27.87%) being higher than planned (15%) and enrollment (N = 183) lower than the planned enrollment (N = 216), the power analysis was based on the actual randomization of 183 participants (SC-TF-CBT=91; standard TF-CBT=92).

**Aim 2.** We used backward stepwise logistic regression with predictors with  $p < .01$ . Besides predictors in the unadjusted model, demographics including children gender, age and race were included in the partially adjusted

model. In addition, three child primary outcomes were added for the full adjusted model.

**Aim 3.** Instead of LDS we used Linear mixed-effect models (LME) with repeated measures were used to detect whether the potential mechanisms of change declined significantly over time and whether the rate of change differed by treatment group with standard TF-CBT coded as 0 and Step One responders coded as 1. Further, we tested mediation and moderated mediation. If moderated mediation was not found mediation was tested with two regression equations: the first equation included mediators regressed on treatment condition and outcome variables at baseline; the second equation included outcomes regressed on treatment condition, mediators, and outcome variables at baseline. If there was no evidence of significant mediation, linear regression model (OLS) was applied to test the linear estimates as predictors for both outcome (TSCYC-PTS and CSDS-P).

**Aim 4.** A cost comparison analysis of SC-TF-CBT and TF-CBT was performed instead of CEA, given the non-inferiority results. We used generalized linear models using a loglink to determine if differences in costs between the two treatments were statistically significant (two-tailed tests). Effect sizes were estimated based on the logged cost values and statistical significance was inferred via bootstrapped estimation (Algina et al., 2006).

